2.1 Assessment and management of risk

This trial is categorised as: Type A = No higher than the risk of standard medical care

The psychological self-help to be used are generally considered to be safe. The EC interventions to be used will be based on providing psychoeducation, tips, advice, and simple strategies that builds on learning of everyday skills and is unlikely to be iatrogenic. Several elements of the EC self-help, including the targeting of rumination and attributional retraining have already been examined in a number of RCTs with no report of adverse events (e.g., Cristea et al., 2015; Hall et al., 2006; Perry et al., 2014; Topper et al., 2017) including in self-help formats. The focus of the self-help apps is on targeting general emotional competence skills (including appraisals of emotions, emotion regulation and emotional perception and understanding), i.e., it targets a non-medical condition, and is compatible with support of general emotional fitness and general well-being.

Other than the intervention failing to produce an effect, there is nothing in the literature to suggest possible adverse effects for the young adults involved. Versions of components within the EC self-help have been previously used with no detected harmful effect. As with all psychological approaches, individuals reflect on their difficulties, which can produce temporary increases in distress, but no more than would commonly occur in daily life. Prior work has provided positive feedback on the rumination intervention and indicated benefits over 12 months, with no serious adverse events reported: similar positive effects are found for attributional retraining and mind-set interventions, as such, these components of the trial may benefit individual participants. The likeliest outcome for users who do not find the intervention of benefit is their disengagement from it. In addition, participants receive more intensive monitoring, with processes to identify and direct all relevant participants to potential sources of help (e.g., youthinmind.info; Samaritans, General Practitioners; Teléfono de la Esperanza; contact list for child and adolescent psychotherapists in Germany provided by the German Federal Chamber of Psychotherapists; Bündnis Gegen Depression; FIDEO) including in response to reports of thoughts of suicide or self-harm.

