10.3.2 Primary analysis

The primary outcomes (WEMWBS (ECoWeB-PROMOTE); PHQ-9 (ECoWeB-PREVENT) and secondary outcomes will be compared at 3-month follow-up. The primary and secondary continuous outcomes will be reported descriptively (mean and standard deviation (SD)) and inferential comparisons will be reported between the three treatment contrasts ((1) usual practice plus personalised digital self-help EC vs. usual practice alone; (2) usual practice plus non-personalised automated digital CBT self-help vs. usual practice alone; (3) usual practice plus personalised digital self-help EC vs. usual practice alone; (3) usual practice plus personalised digital self-help EC vs. usual practice plus non-personalised automated digital CBT self-help) using linear modelling. All analyses will be based on an intention to treat principle (i.e. according to original allocation irrespective of intervention adherence) and will include participants with complete outcome data at 3-month follow-up, and will adjust for baseline outcome score (where relevant) and minimisation variables (age, gender, country). Furthermore, we will adjust for any baseline participant characteristics that are substantively unbalanced at baseline (defined as a difference ≥ 10 percentage points across categories for a categorical variable, or a difference in means >1 SD for continuous variables), and if the characteristic is thought to be predictive of outcome. Binary secondary outcomes (occurrence of major depressive disorder; generalized anxiety disorder) will be reported as proportions and analysed used logistic regression.

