#### 3.3 Randomisation

Within both PROMOTE and PREVENT separately, participants will be allocated to one of the three interventions in a 1:1:1 ratio using a minimisation algorithm to promote balance across the arms overall and within minimisation factors. The minimisation factors to be used are gender (categorised as male:female:both:neither anticipated to be recruited in a 20:70:5:5 ratio), age (categorised as 16–17:18–22, anticipated to be recruited in a 20:80 ratio), and country of residence (UK:Germany:Spain:Belgium, anticipated to be recruited in a 28:28:28:18 ratio). The first 50 randomisations (for both trials) will be performed using simple randomisation; subsequent randomisations will use the minimisation algorithm, taking account of the previous allocations. Further details of the randomisation procedure are provided elsewhere (Trial selection, randomisation, selection of emotional competence intervention components document).

Randomisation across all countries will be carried out by ExeCTU. The randomisation algorithm will be automatically invoked when the participant has submitted the required baseline data and provided consent. The participant will be immediately informed of the allocated treatment and the downloaded version of the app will provide the appropriate intervention. There is no possibility for a participant to receive a version of the app other than the version to which the participant was randomly allocated.

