## 6.3 Analysis methods

All continuous outcomes will be reported descriptively (mean, SD) at all follow-up timepoints. Inferential analyses The primary analyses for the primary and continuous secondary outcomes will use linear regression models with adjustment for baseline score, age (as a continuous variable rather than the dichotomised minimisation variable), country, and any other participant characteristics observed at baseline to be unbalanced across treatment arms (meeting the criteria set out in Section 5.5). The primary follow-up time will be at 3 months; analysis of 12-month follow-up data will also be performed using the same approach. The primary analyses will be based on an intention to treat (ITT) approach (i.e. all participants will be included in the analyses according to their randomised allocation) and will use observed data only.

As a secondary analysis, we will perform repeated measures analyses (using a mixed effects linear regression model with a random effect on participant) for primary and secondary continuous outcomes, including data from participants with observed data for at least one of the three follow-up timepoints. Analyses will be performed to compare both active interventions with usual care, and to compare the personalised active intervention with the standard active intervention. A fixed effect interaction between timepoint and trial arm will be used to evaluate differential treatment effects across timepoints. Adjustments for baseline covariates will be made as for the primary analysis regression models; baseline score will be included as a covariate. Binary outcome measures will be analysed using logistic regression models with adjustments for covariates as above.

The primary analyses will use only the data collected during the time window. The amount of such data will be determined, with the possibility of performing a sensitivity analysis should the amount of data collected outside the time window be substantive. These analyses will be performed using observed data for the ITT population (i.e. according to initial random allocation). No formal adjustments of p-values for multiple testing will be performed; the results for the primary outcome will be interpreted first and the results of the secondary outcomes will then be interpreted in the light of multiple testing. The results of all descriptive and inferential analyses for the primary and secondary continuous outcomes are set out in Tables A.4–A.10.

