#### 6.10 Adverse events

The main anticipated adverse event in this trial is deliberate self-harm. Serious adverse events will be reported descriptively by treatment arm, also the number of participants in each treatment arm who have experienced at least one serious adverse event will be reported. Inferential analyses will also be performed using the count of events (Poisson or negative binomial model) and the number of participants experiencing the outcome at least once during the 12-month follow-up period (logistic regression), using observed data on an ITT principle with adjustment for covariates as for the outcome data analyses (Table A.14).

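### SAP 6.10 has no rule for sparse serious adverse events: if an arm has none, its planned logistic and Poisson or negative binomial models give no finite odds ratio or rate ratio against that arm

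*SAP*

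**What the plan says.** SAP 6.10 first plans descriptive reporting of SAEs by arm, including the number of participants with at least one. It then adds: "Inferential analyses will also be performed using the count of events (Poisson or negative binomial model"), with logistic regression for having at least one event in 12 months. Both are to be fitted "using observed data on an ITT principle with adjustment for covariates as for the outcome data analyses".

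The outcome models in SAP 6.3 are fitted "with adjustment for baseline score, age (as a continuous variable rather than the dichotomised minimisation variable), country" and any characteristic found unbalanced at baseline. Protocol 10.3.2 says the analyses "will adjust for baseline outcome score (where relevant) and minimisation variables (age, gender, country"). Gender is therefore a covariate in the protocol but is not listed in SAP 6.3, and the protocol gives the SAP precedence on analysis detail.

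Table A.14 provides for an incidence rate ratio, an odds ratio and a global p-value for each adverse outcome, with the outcomes still to be coded. SAP 6.11 names Stata version 14 or later but no command or option. SAP 6.2 lists only descriptive SAE data among the purposes of the analysis. Neither document gives an expected SAE rate, a minimum number of events for modelling, or an exact or penalised alternative.

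**The concern.** The models chosen need events in every arm to return a ratio. A safety reader most needs a number when events occur on an app and none occur on usual practice, and there these models return nothing usable.

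The documents give reason to expect few events, without quantifying them. SAP 3.6 calls the intervention low risk. Protocol 2.1 reports that earlier work on the rumination component "indicated benefits over 12 months, with no serious adverse events reported". SAP 6.10 names deliberate self-harm as the main anticipated event, while Protocol 6.2 excludes active suicidality and past depression. Any single coded row of Table A.14 will be rarer than all SAEs together.

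Without a rule, the analyst must choose a substitute method after seeing the events by arm. SAP 1.7 treats changes made after scrutiny of the data and unblinded interpretation as post hoc. A smaller defect sits in the same sentence: adjusting as for the outcomes brings in a baseline score, which an SAE does not have.

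**Working it through.** The plan states no figure for SAE risk or SAE power, so there is none to reproduce. The check asks how likely an empty arm is, what the models do then, and what the alternative returns.

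**Inputs**
- Cohort 3599 (SAP 6.9), split 70:30 (SAP 3.4), 1:1:1 allocation (SAP 3.3). PROMOTE: 0.70 × 3599 ≈ 2519, about 840 per arm. PREVENT: 0.30 × 3599 ≈ 1080, 360 per arm.
- Observed fraction 60%. This borrows the 40% attrition planned for 3 months; the SAE analysis covers 12 months, so it is an assumption. It gives 0.6 × 840 = 504 per arm (1512) and 0.6 × 360 = 216 per arm (648).
- SAE risk p per participant over 12 months, the same in every arm: assumed, shown as a range.

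**Chance that at least one arm has no events**

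P = 1 − [1 − (1 − p)^n]³, with n the number per arm.

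| Trial, n per arm | p = 0.5% | p = 1% | p = 2% |
|---|---|---|---|
| PREVENT, 216 (60% observed) | 71% | 30% | 4% |
| PREVENT, 360 (all observed) | 42% | 8% | 0.2% |
| PROMOTE, 504 (60% observed) | 22% | 2% | below 0.1% |

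Worked example, PREVENT at 1%: 0.99^216 = 0.114, the chance that one named arm, such as usual practice, is empty. Then 1 − (1 − 0.114)³ = 0.30. The expected total is 648 × 0.01 ≈ 6.5 participants with an event.

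**What the models do with an empty arm**

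Maximum-likelihood fits with arm, country and age were run on simulated PREVENT-size data (214 per arm).
- *One app arm empty (events 2, 0, 3):* the logistic fit failed with a singular matrix. The Poisson log rate ratio for the empty arm ran to −21 with a standard error of about 18,700. The other app arm against usual practice stayed finite (0.52, SE 0.92).
- *Usual practice empty (events 0, 3, 2):* both app-versus-usual-practice coefficients diverged, to about 34 to 35 in the logistic model (SE above 24 million) and 21 to 22 in the Poisson model (SE about 16,500).

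A negative binomial model has the same log-linear mean and the same problem.

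**What the models do with an empty country**

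With country as a factor, the fitted risk in a zero-event country goes to zero whatever the arm effect, so that country carries no information on the arm contrast. Check on simulated data (648 participants, one country of 97 with no events): the logistic arm log odds ratios were −0.275 and −0.728 (SE 0.779, 0.879) with that country kept, and identical with it removed. The Poisson estimates were also unchanged (−0.266 and −0.708).

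**What the alternative returns**

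Illustration: 0/214 against 3/214.
- Risk difference 3/214 − 0 = 1.4 percentage points; Newcombe 95% CI −0.6 to 4.0.
- Exact upper 95% limit for the empty arm: 1 − 0.025^(1/214) = 1.7%.
- Firth odds ratio: (0.5/214.5) ÷ (3.5/211.5) = 0.14, penalised profile 95% CI 0.001 to 1.47.
- Fisher exact p = 0.25.

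**The case against.** The strongest objection is that rarity is assumed. No SAE rate is stated, and low risk in SAP 3.6 is not an event count. Ascertainment is broad: the question in Protocol 16.5 covers health emergencies, accidents and unplanned admissions from any cause, and the SAE form in Appendix 16.1 lists hospitalisation and new disorders. If all-cause SAEs reach 2%, an empty arm is unlikely in PREVENT (4%) and negligible in PROMOTE; at 3% the PREVENT figure is 0.4%. Events also reach the team by email and telephone, so 60% may understate what is observed. This stands. It makes the size conditional, and it weighs less for single coded rows of Table A.14.

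Second, the counts and proportions by arm come first in SAP 6.10 and the models are additional, so three events against none would be visible. This also stands. It limits the harm to the inferential part but does not give that part a working method.

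Third, on baseline score, Protocol 10.3.2 says where relevant. That is a reasonable reading, but SAP 6.3 and 6.10 do not repeat it.

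A reader might go further and infer that a country, or a small gender category, with no events also breaks the treatment comparison, or that participants silently leave the intention-to-treat set. The documents do not support this. The arm contrasts stay finite and unchanged. A logistic routine that removes perfectly predicted levels would show a smaller N, but Poisson drops no one. The documents describe no software behaviour, and SAP 6.3 does not list gender. Nor should a numerical ceiling on the SAE risk be drawn from the remark in Protocol 2.1, which does not identify the study or its SAE definition.

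**Conclusion.** The point holds for an empty arm only. In that pattern the inferential analysis in SAP 6.10 cannot give an odds ratio or rate ratio for any contrast with the empty arm, and there is no pre-specified alternative.

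How likely that is depends on an SAE risk that the documents do not state. For PREVENT it is a real prospect at 1% or below (8% to 30% at 1%, 42% to 71% at 0.5%, depending on the fraction observed). For PROMOTE it becomes appreciable nearer 0.5% (22% with 60% observed). At 2% or above it is a minor matter for all SAEs combined. These figures assume equal risk across arms, a 70:30 split of 3599, and 60% or 100% observed.

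The change should be made: the model is committed to, the failing pattern is plausible, and the better method is nearly free. The safety data would still be reported descriptively without it.

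**What to change.** In SAP 6.10 and Table A.14:

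1. Make the main SAE comparison unadjusted: n/N by arm, with the risk difference and its exact or Newcombe 95% confidence interval for each of the three contrasts.
2. Where a model is reported and events are few or an arm has none, use Firth penalised or exact logistic regression with arm only, and an exact rate ratio for counts. State now the event count below which this applies.
3. Remove baseline score from the SAE models.
4. Do not make adjusted models conditional on every covariate level having events. An empty country does no harm to the arm contrast, and such a rule would let the data choose the model.
5. Reconcile SAP 6.10 with SAP 6.2, which lists SAE data as descriptive only.

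This changes analysis wording only; data collection and participant management are untouched. The cost is that rare events are compared without covariate adjustment, which loses almost no precision.

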#### 6.11 Statistical software

All statistical analyses will be performed using Stata v.14 (or later).

#### 7. General analysis considerations

#### 7.1 Timing of analyses

The first set of statistical analyses will be performed when the 3-month outcome data is available and the database has been locked. At this point, the statistician will perform the 3-month inferential analyses (as well as descriptive analyses for 1- and 3-month data), whilst being unaware of treatment arm allocation. These analyses will be performed on the ITT population using observed data only. Following presentation of the results with anonymised allocations, the allocations will be revealed for interpretation of the results. Following revelation of treatment allocations, the remaining analyses of 3-month outcome data will be performed. Following completion of 12-month data collection and database lock, the remaining analyses of the 12-month outcome data will be performed. At this point the repeated measures analyses and analyses including imputed and observed data will be performed.

#### 7.2 Related documents

The related documents that should be read in conjunction with this SAP are set out below.

- 1. Trial protocol version 1.3
- 2. Trial master file (TMF)
- 3. Trial selection, randomisation, selection of emotional competence intervention components document
- 4. Data Management Plan
- 5. Process evaluation analysis plan
- 6. SOP 019 Deviations, Misconduct and Serious Breaches of GCP and(or) the Protocol

## 7.3 Mediation analyses

Quantitative mediational analyses will be described in the process evaluation analysis plan.

## 8. Health economic analysis plan

### 8.1 Aim of economic evaluation

Both trials seek to evaluate mental health and emotional wellbeing within their respective participant samples comparing two active interventions (one personalised, one uniform across participants) against usual care (self-monitoring of emotional well-being via an app) and against each other. The aim of the health economic evaluation is to estimate costs and outcomes associated with the interventions.

## 8.2 Objective of economic evaluation

To undertake within country cost consequence analyses

#### 8.3 Overview of economic analysis

The economic analyses will use a cost-consequence approach. Because all the resources used, costs, and outcomes are transparently listed in the cost-consequence analysis, decision makers can select the information that is of most interest to them. Furthermore, the choice of cost-consequence analysis supports current approaches used by healthcare decision-makers to value the efficiency of healthcare interventions across Europe.[6]

#### 8.4 Jurisdiction

A cost consequence analysis will be present for each country.

#### 8.5 Perspective

The analyses will take a societal perspective.

#### 8.6 Time horizon

12 months.

#### 8.7 Identification of resources

Health and social care utilisation will be identified and collected using an adapted version of the Adult Service Use Schedule (AD-SUS). Developed for mental health trials the AD-SUS questionnaire quantifies the use of healthcare resources, use of medication and employment and time off work over the trial including follow up.[7] Adaptation will include time away from school or college together with changes to the wording to ensure relevance across the four countries.

#### 8.8 Measurement of resource use data

The AD-SUS will be administered at baseline to assess use of services in previous 6-months, at 3month follow-up, ask about use of services since the baseline interview, and 12-month follow-up, ask about use of services since the 3-month interview.

## 8.9 Valuation of resource use data

Unit costs of health and social care will be taken from appropriate national publications to reflect differences in costs between countries (for example, Curtis & Burns (2018)).[8] Productivity losses will be valued using the human capital approach.[9] Wage rates for each country will be derived from European sources such as Eurostat.[10]

### 8.10 Identification of outcomes

The analysis will use the EQ-5D-3L.[11]

## 8.11 Measurement of outcomes

The EQ-5D-3L will be administered with the adapted ADSUS at baseline, 3 and 12-months

#### 8.12 Valuation of outcomes

Responses to the EQ-5D-3L will be converted to utility values using the EuroQoL general population tariff values for each country.[12–15]

#### 8.13 Analysis population

The analyses will be on the intention to treat (ITT) basis (i.e. participants will be included in the analyses according to their randomised allocation) and will include observed data only).

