3.4 Primary endpoint/outcome

The primary endpoint of the trial is at 3 months post randomisation.

All participants will have had the opportunity to use the App for 3 months at their own discretion so at that point the trial is powered to see if the personalised Emotional Competence self-help is superior to the CBT self-help (active control) and to the usual care self-monitoring control in promoting well-being (ECoWeB-PROMOTE trial) or preventing poor mental health (ECoWeB-PREVENT trial). The 3month primary endpoint was chosen:

a. to maximise power and sensitivity to intervention as closer to actual use of intervention

b. to reduce the negative impact of drop-out attrition on study power

c. to increase comparability to other studies using mental health apps as this is a typical endpoint in app interventions

d. to provides a proof-of-principle of changes in known predictors/analogues of poor mental health such as depression and anxiety – i.e., if we can show change in depression symptoms, rumination or other EC measures at 3 months, then we are likely to predict the future impact of the intervention on the onset of future emotional disorders. This can be checked at the 12month follow up (i.e., this is consistent with a prevention-mechanism trial – Zalta & Shankman 2016). Prevention Mechanism trials are deemed successful if an intervention reduces well-established risk factors for development or maintenance of psychopathology or increases established resilience factors. Such trials may help identify novel interventions that target multiple known risk factors, and in turn, strategies most likely to reduce dysfunction.

e) there is an expectation of relatively high attrition by the 12month follow-up due to competing demands on the attention and motivation of young adults. The Youth Advisory Board advised that staying in the trial for 3 months would be reasonable, but they might lose interest over a longer period. The highest number of participants returning follow ups is likely to be at 3 months.

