10 STATISTICS AND DATA ANALYSIS

10.1 Sample size calculation

The overall sample size for EcoWeb is predicated on recruiting an overall cohort of potential participants that will have adequate sample size to allow us to recruit to each of the two RCTs (ECoWeB-PROMOTE; ECoWeB-PREVENT). Once these trial sample sizes are determined, the size of an overall cohort of potential participants will be selected using expected proportions of potential participants that will be eligible for each of the two trials.

Each of the two trials includes the following three arms: (i) usual practice including self-monitoring plus offer of personalised digital EC self-help; (ii) usual practice including self-monitoring plus offer of non-personalised digital CBT self-help; and (iii) usual practice including self-monitoring (i.e., continuing in cohort).

The following sample size calculations for each trial are based on a 2-arm comparison and three analytical contrasts (arm i vs arm iii or arm ii vs. arm iii or arm i vs. arm ii), with no adjustment for multiple testing (for example, by adjustment of the alpha threshold). All sample size calculations are based on a 2-sided test with 90% power, an alpha threshold of 0.05, and 40% attrition at 3-month follow-up (e.g., Topper et al., 2017).

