#### 6.5 Missing data

Demographic characteristics of participants who do not provide data for the primary outcome measure of their trial at 3- and 12-month follow-up will be set out (including participants who have

formally withdrawn (but allowed their previously collected data to be used), and participants not formally withdrawn but did not complete the primary outcome at follow-up) (Tables A.12 and A.13).

Multiple imputation using chained equations (MICE) will be used to impute primary and secondary continuous outcomes. Predictive mean matching will be the method for imputing individual scores; the number of imputed datasets will be determined by the percentage of participants in each trial that have missing 3-month outcome data (i.e. WEMWBS for PREVENT, PHQ-9 for PROMOTE). Imputation models will be informed by treatment arm, baseline scores, other covariates to be included in the model (i.e. minimisation covariates), and other baseline characteristics found to predict outcome or propensity for missingness (logistic regression models will be used to investigate the associations between baseline characteristics and missingness). Regression models using the imputed datasets will be performed using the same methods as described in Section 6.3 for the ITT population (Tables A.4–A.10). Analyses using imputed data will be considered as a secondary analysis.

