## 8.16 Analysis of resource use, costs and outcomes

Within country analyses of the differences between the trial arms will be undertaken. Although the distribution of costs is commonly skewed in populations of this kind, analyses will compare mean costs between groups using standard parametric regression models adjusted for minimisation variables and baseline costs. The robustness of the parametric tests will be confirmed using bias-corrected, non-parametric bootstrapping.[16,17] As with primary and secondary outcomes, between group differences in costs and EQ-5D-3L will be presented as means and 95% CIs using STATA v14.2.

Given the differences in cost structures (health and social care, and wage rates) and differences in the population tariffs between countries, no formal analyses of differences between costs and utility values between countries will be undertaken.[18] However, the differences between the number and type of resource use and days away from work and employment will be examined.

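### The economic analysis uses observed data only and gives costs no imputed sensitivity analysis, although a 12-month cost needs two consecutive service-use forms

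*SAP*

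**What the plan says.** SAP 8.13 defines the economic population by randomised allocation "and will include observed data only". The time horizon is 12 months (SAP 8.6). Under SAP 8.8 the AD-SUS at 3 months is to "ask about use of services since the baseline interview, and 12-month follow-up, ask about use of services since the 3-month interview". Costs are compared using "standard parametric regression models adjusted for minimisation variables and baseline costs", and SAP 8.16 adds: "Within country analyses of the differences between the trial arms will be undertaken".

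No missing-data method or sensitivity analysis for costs appears in SAP section 8 or in protocol 10.8. For clinical outcomes, SAP 6.5 states: "Multiple imputation using chained equations (MICE) will be used to impute primary and secondary continuous outcomes". It classes the imputed results as secondary. Table A.8 accordingly has a row for observed and imputed EQ-5D-3L data.

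On expected loss, protocol 10.1 says: "All sample size calculations are based on a 2-sided test with 90% power, an alpha threshold of 0.05, and 40% attrition at 3-month follow-up". Protocol 3.4 adds that "there is an expectation of relatively high attrition by the 12month follow-up", without a figure. Protocol 7.7 limits telephone follow-up to the primary outcome measures.

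**The concern.** The two follow-up AD-SUS forms do not overlap: one covers months 0 to 3, the other months 3 to 12. An observed total for the 12-month horizon therefore exists only for people who return both. Telephone contact collects neither AD-SUS nor EQ-5D, so these can be no more complete than the primary outcome, and will be less complete wherever the telephone is used.

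Two things are at stake. The first is precision, because costs are usually skewed and each trial is split by country as well as by arm. The second is bias. If those who return both forms differ in service use from those who do not, and differ to a different degree by arm, the observed cost difference is distorted and the plan offers nothing to set beside it. Protocol 10.3.3 already argues that imputation adds power when much is missing and carries the lowest risk of bias. That argument applies at least as strongly to a variable that depends on two visits.

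**Working it through.** **Inputs.** Planned retention at 3 months r3 = 60% (protocol 10.1); expected retention 70% (protocol 7.8). Retention at 12 months, r12, is not given, so the values below are assumptions. Revised total 3599 (SAP 6.9); 70% PROMOTE and 30% PREVENT, three equal arms (SAP 3.4, 3.1); country ratio 28:28:28:18, which sums to 102 (SAP 3.3).

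**The plan's own figures.** There is no economic sample size to reproduce. The clinical ones do reproduce. For PROMOTE, 2 × (1.960 + 1.282)² × 11.3² / 3.0² gives 299 per arm, against 300 stated; 300 / 0.60 = 500. For PREVENT, the same formula with 5.4 and the protocol's 2.59 gives 92, against 93 stated; 93 / 0.60 = 155. The 40% loss is therefore used as described, and applies to 3 months only.

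**Share with both follow-up forms.** Nested loss (nobody who misses 3 months returns at 12): min(r3, r12). Independent loss: r3 × r12. Least possible overlap: max(0, r3 + r12 − 1).

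| r3 | r12 (assumed) | Nested | Independent | Least overlap |
|---|---|---|---|---|
| 60% | 60% | 60% | 36% | 20% |
| 60% | 50% | 50% | 30% | 10% |
| 60% | 40% | 40% | 24% | 0% |
| 70% | 70% | 70% | 49% | 40% |
| 70% | 60% | 60% | 42% | 30% |
| 70% | 50% | 50% | 35% | 20% |

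Whatever r12 is, the share cannot exceed r3. At the planned 40% loss, at least 40% lack a complete 12-month cost. Protocol 7.8 reports that earlier studies lost most people at the first follow-up and few afterwards. With its expected 30% loss, that is close to the nested 70%/70% row, so about 30% or slightly more would lack a complete cost.

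**Country cells at the revised target.**
- PREVENT: 3599 × 0.30 / 3 = 360 per arm. Large country: 360 × 28/102 = 99. Belgium: 360 × 18/102 = 64.
- PROMOTE: 3599 × 0.70 / 3 = 840 per arm. Large country: 840 × 28/102 = 231. Belgium: 840 × 18/102 = 148.

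Complete cost records per arm, from unrounded cell sizes:

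| Trial and country | 36% complete | 60% complete | 70% complete |
|---|---|---|---|
| PREVENT, each large country | 36 | 59 | 69 |
| PREVENT, Belgium | 23 | 38 | 44 |
| PROMOTE, each large country | 83 | 138 | 161 |
| PROMOTE, Belgium | 53 | 89 | 104 |

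The baseline form, needed for the baseline-cost covariate, should seldom bind, because randomisation follows the baseline assessment.

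**The case against.** A reader might infer four stronger things, and each meets a fair answer.

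- **Most participants will be dropped.** This is not shown. No 12-month retention or AD-SUS completion rate is given. Protocol 3.4 expects high loss at 12 months, but protocol 7.8 expects 30% at 3 months, treats 40% as a safety margin, and reports little later decline. More than half are lost only if 12-month retention falls below 50% or the two forms are largely missed by different people.
- **Clinical outcomes are imputed and costs are not.** This overstates the contrast. The primary clinical analysis is also observed-only (SAP 4.3, 6.3), and imputation is secondary there. What remains is that costs lack even that secondary analysis.
- **People with one form are discarded.** The SAP never defines the total-cost variable. In a cost-consequence analysis, costs for 0–3 and 3–12 months could be reported separately, which would keep these people. The SAP does not say this will be done, so the gap is one of definition as well as of missing data.
- **SAP 8.13 contradicts Table A.8 on EQ-5D-3L.** Section 8 concerns country-tariff utilities within country, and Table A.8 has an observed-data row too, so this is not a flat contradiction. Nevertheless, SAP 6.1 lists the adapted AD-SUS among outcomes that it calls continuous, SAP 6.5 imputes continuous secondary outcomes, SAP 8.13 allows observed data only, and Tables A.4–A.10 contain no AD-SUS table. An analyst could not be sure which rule governs.

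Two further points stand. Small country cells come mainly from the within-country design rather than from SAP 8.13. Protocol 10.3.3 also concedes that missing at random may not hold.

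**Conclusion.** The point holds as a modest, inexpensive improvement. The documents establish that costs are analysed on observed data only, that a 12-month total needs both follow-up forms, that the telephone route recovers neither, and that no imputed cost analysis is planned.

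The firm figure is that at least 40% would lack a complete 12-month cost at the planned 3-month loss. The 36% to 60% range for having both forms assumes 40% loss at 12 months as well, with independence at one end and nesting at the other. On the more favourable pattern in protocol 7.8 the loss is about 30% or slightly more. The cell counts also assume the anticipated country and trial splits.

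The documents do not support saying that the cost results will rest on a minority of participants. Nor do they show the direction of any bias.

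**What to change.** In SAP 8.13 and 8.16:

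1. Define the 12-month cost as the sum of the 0–3 and 3–12 month costs.
2. Keep the observed-data analysis.
3. Add, as a secondary or sensitivity analysis, multiple imputation by chained equations of period-level costs and EQ-5D utilities, with the predictive mean matching already chosen in SAP 6.5.
4. Run it within country, or impute resource use and then apply country unit costs. A single pooled matching model could borrow donor costs from countries whose cost structures SAP 8.16 treats as too different to compare formally.
5. Impute separately by arm or include arm in the model, with the minimisation variables, baseline cost and utility, and the other period's cost.
6. Report the imputed result beside the observed one and state that it assumes missing at random.
7. Reconcile SAP 8.13 with Table A.8, and say whether SAP 6.5 covers the AD-SUS.

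The cost is SAP wording, some extra analysis, and longer run time where bootstrapping is combined with imputation. No new data are needed. Imputation models may need simplifying in the smallest country cells. The economic analysis waits for the 12-month lock (SAP 8.14), so the change can precede it. It is best made before allocations are revealed after the 3-month analysis, since SAP 1.7 treats later revisions as post hoc.
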